4.0 SUBJECT ENROLLMENT

4.1 Screening and recruitment

Patients:

- Acutely ill patient is screened and recruited as above.
- If participant agrees, the RHH MD will further describe the program, answer initial questions, and further assess whether the participant meets inclusion/exclusion non-clinical (e.g., social) and clinical criteria (please see the subject eligibility checklist)

Clinicians

- Members of the rural home hospital clinical team (MD, RN, paramedic, NP) that have expressed interest in participating in research activities and meet inclusion criteria will be approached by a member of the study team.

4.2 Methods of enrollment and procedures for obtaining consent/ informed consent

Clinicians:

- If the clinician meets inclusion criteria, then the study team will invite them to participate. The research assistant will explain the purpose of the study, answer initial questions, and seek written informed consent from clinician participants.

Patients:

- If the participant has interest in the program and meets inclusion/exclusion criteria, the MD (either over the phone or via a live video visit) or NP will obtain written informed consent of the participant to enroll in the RHH study.
- The MD will make the final decision to admit the patient to home hospital.

[figure not shown]

Figure 1.

4.4 Treatment Assignment

All eligible and agreeable patients will be enrolled in RHH.

5.0 STUDY PROCEDURES

5.1 Study visits and measured parameters

Each day, the RHH clinical team will make in-person and/or virtual visits to the patient's home. These are personnel who have been trained in home health and carry out home health as per the usual care they deliver. The RHH module offers most of the same medical components that are standard of care in an acute care hospital (**Table below**). The typical staff (MD, RN or paramedic), diagnostics (blood tests, vital signs, telemetry), intravenous therapy, and oxygen/nebulizer therapy will all be available for home hospital.

RHH improves upon the components of a typical ward's standard of care in several ways:

- Point of care blood diagnostics (results at the bedside in <5 minutes);
- Minimally invasive continuous vital signs, telemetry, and activity tracking
- 24/7 clinician video visits;
- Ambulatory/portable infusion pumps that can be worn on the hip;

Component	Module		
Personnel	  Nurse/Paramedic 
 • 2 daily visits (1 in-person; 1 virtual) • Medication administration • IV access management • Education 		 Physician 
 • 1 daily interaction • Medical decision making
Diagnostics	Point of care: BMP, Hgb/Hct, PT/INR, ultrasound, x-ray, PFTs, ECG		
Pharmacy	Any inpatient medication, most any route		
Equipment	Ambulatory infusion pump, peripheral IV, oxygen concentrator		
Communication	Telepresence/virtual visits		
Monitoring	Wireless remote vital signs, telemetry, activity tracking		

Table 1.

As denoted in the table above, the physician will make at least one daily virtual visit to the patient's home, facilitated by the nurse/paramedic. At the discretion of the physician and nurse/paramedic, the physician can make additional virtual visits should the patient's clinical condition require it. Similarly, the nurse/paramedic will make at least two daily visits to the patient's home. At the discretion of the physician and nurse/paramedic, the nurse/paramedic can make additional visits should the patient's clinical condition require it. This will be an ongoing twice daily discussion among clinicians, patient, and caregivers, as applicable. A patient or clinician can initiate a video visit at any time. As denoted in the table above, the RHH team uses a suite of communication software to communicate with the patient and among team members.

For patients with chronic/stable dementia, they will receive mental status assessments (eg, Confusion Assessment Method) by the home hospital RN/paramedic at each visit (at least 2 daily). As is standard of care, we will take measures to avoid delirium: open blinds to allow light in during the day, minimize environmental noise, encourage typical routines to optimize eating and sleeping, and reassess medication list for culprit medications.

Clinical parameters measured will be at the discretion of the physician and nurse/paramedic, who treat the participant following evidence-based practice guidelines, just as in the usual care setting. Monitoring and data collection will be performed by RHH clinicians. The clinical home hospital team manually checks vital signs at least daily. If deemed necessary based on a patient's acuity, the home hospital team can visit additional times. At all times, the patient and care team have 24/7 access to the RHH attending physician.

On top of this "on-the-ground" team, the home hospital attending is notified with an alarm should there be delayed data transfer. Such an alarm would cause the attending to contact the patient as deemed clinically appropriate.

Please see below for all collected data points.

Documentation by RN/paramedic and MD will occur via digital intake notes, daily progress notes, and discharge notes that will be compiled (on a secure shared drive) and uploaded as a scanned document to the patient's chart upon discharge.

[figure not shown]

Figure 2 RHH flow. Note a patient may **enter** this flow from their home, a clinic, the emergency department, or the hospital floor. The patient is **triaged** by the RHH nurse with as needed assistance of the RHH MD. The RHH nurse/paramedic **deploys** in the patient's home, facilitates a medical evaluation by a remote MD, welcomes and educates the patient, and sets up monitoring and communication technology. The nurse **rounds** at least once to twice daily in person, facilitating an interaction with the RHH MD. Finally, the patient is **discharged** using the same criteria for discharge as would be used in a traditional hospital (ability to perform activities of daily living given supports in the home).

5.2 Drugs to be used

Only medications used in the usual care of hospitalized patients will be used. For example, a patient with pneumonia might receive guideline-based antibiotics with ceftriaxone and azithromycin.

5.3 Devices to be used

- Home hospital employs standard devices during the usual care of hospitalized patients. For example, a nebulizer machine.
- Home hospital additionally employs
 - Vital signs monitoring patch: Vital Connect VitalPatch (FDA cleared application/use) or BioIntellisense BioSticker (FDA cleared application/use)
 - Ambulatory infusion pump: Smiths Medical CADD Solis VIP (FDA cleared application/use)
 - Point of care diagnostic meter: Abbott iSTAT (FDA cleared application/use) or Siemens EPOC (FDA cleared application/use)

5.4 Procedures/surgical interventions

- Home hospital employs the same standard procedures used during the usual care of hospitalized patients. For example, peripheral venipuncture. Need for surgery is an exclusion criterion.

5.5 Data to be collected and when the data will be collected

5.5.1 Primary endpoint

Outcome measure	Data sources	Day(s) Obtained
RHH admission, daily care, and discharge processes accomplished	Process checklist (attachment) and semi-structured interviews with clinicians	Daily

5.5.2 Secondary endpoints

Outcome measure	Data sources	Day(s) Obtained
3-item Care Transition Measure	RA via patient	Within 1 week of discharge
Picker Experience Questionnaire	RA via patient	Within 1 week of discharge
Global satisfaction	RA via patient	Within 1 week of discharge
Perceived acceptability of RHH care	Post-discharge semi-structured interviews with clinicians, patients, and caregivers	Within 1 month of discharge
Perceived safety, quality of care, caregiver burden	Post-discharge semi-structured interviews with clinicians, patients, caregivers	Within 1 month of discharge
Escalation of care to hospital	RA via RN/EMTP	Daily
Adverse event*	RA via RN/EMTP	Daily
Unplanned mortality during admission	RA via RN/EMTP	Daily

Lab Orders, #	RA via RHH records	Daily
Length of stay	RA via RHH records	Discharge
Unplanned readmission(s) after index, # and y/n	RA via patient	30-days post-discharge
ED visit(s) after index, # and y/n	RA via patient	30-days post-discharge

*: see appendix

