3.0 SUBJECT SELECTION

3.1 Inclusion

Patient inclusion criteria:

Patient clinical inclusion criteria:

- ≥ 18 years old
- Any infectious process (e.g., pneumonia, diverticulitis, cellulitis, complicated urinary tract infection)
- Heart failure exacerbation
- Asthma and chronic obstructive pulmonary disease exacerbation
- Atrial fibrillation with rapid ventricular response
- Diabetes and its complications
- Venous thromboembolism
 - This includes a patient who requires therapeutic anticoagulation and concomitant monitoring (thus requiring inpatient status)
- Gout exacerbation
- Chronic kidney disease with volume overload
- Hypertensive urgency
- End of life / desires only medical management
 - Regarding a patient who desires only medical management, this includes a patient who requires acute care for symptom management but declines any surgical intervention. This may include a patient who is about to transition to hospice care, for example, but still has the functional capacity to meet our criteria below. Under these circumstances, we would make sure that various contingencies, including possible transition to hospice care or hospital readmission, are completely understood by patients and caregivers as applicable.

Patient social inclusion criteria:

- Lives in rural or ultra-rural area (see definitions in Appendix) that can be served by one of our RHH clinicians.
- Has capacity to consent to study
- Can identify a potential caregiver who agrees to stay with patient for first 24 hours of admission. Caregiver must be competent to call care team if a problem is evident to her/him. After 24 hours, this caregiver should be available for as-needed spot checks on the patient.
 - This criterion may be waived for highly competent patients at the patient and clinician's discretion.

Patient caregiver inclusion criteria: (not required for patient participation):

- Age \geq 18 years old
- Has capacity to consent to study
- Lives with or nearby to patient

Clinician inclusion criteria:

- Any member of the rural home hospital (RHH) clinical team (MD, RN, paramedic, NP) who will be participating in the screening and recruitment of patients for the rural home hospital intervention and/or providing care to rural patients that enroll in the intervention.

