3.3 Source of subjects and recruitment methods

All subjects will be associated with the University of Utah Health system. The University of Utah Health has agreed to serve as research collaborator.

A patient may be considered for RHH care if they are acutely ill at home, present acutely ill to a clinic or emergency department, or if they are admitted and require additional days of acute care (“early transfer”):

- If at home: this patient phenotype is well-known to her/his physician and has an acute illness of highly likely etiology (e.g., heart failure or chronic obstructive pulmonary disease exacerbation). The patient’s care team (perhaps primary care or a specialist) will receive a call from the patient describing acute symptoms. The care team will call the RHH nurse practitioner (NP) to describe the case. If appropriate, the RHH NP will call the patient to determine eligibility and interest. If eligible, the RHH MD will make the decision to admit and the MD or NP will consent the patient.
- If presenting acutely ill to a clinic: after appropriate assessment by the clinic care team, and if the team believes the patient requires admission, the clinic care team will call the RHH NP to describe the case. If appropriate, the RHH NP will call the patient to determine eligibility and interest. If eligible, the RHH MD or NP will consent the patient. The patient will be transported home in an appropriate transport (personal car, chair car, or ambulance). The RHH nurse/paramedic will meet the patient in their home.
- If presenting acutely ill to an emergency department: after appropriate assessment by the emergency department team, and if the team believes the patient requires admission, the emergency department care team will call the RHH NP to describe the case. If appropriate, the RHH NP will call the patient to determine eligibility and interest. If eligible, the RHH MD or NP will consent the patient. The patient will be transported home in an appropriate transport (personal car, chair car, or ambulance). The RHH nurse/paramedic will meet the patient in their home.
- If admitted and requiring additional days of acute care (“early transfer”): an ideal patient for this setting is a patient with a heart failure exacerbation requiring additional days of IV diuresis and close monitoring including daily electrolyte and telemetry monitoring. Patients who require additional days of acute care but could be cared for with RHH will

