5.5.3 Covariates of Interest

Outcome measure	Data sources	Day(s) Obtained
Age	RA via patient	Admission
Gender	RA via patient	Admission
Race/ethnicity	RA via patient	Admission
Primary language	RA via patient	Admission
Health insurance status, public/private/none	RA via patient	Admission
Comorbidities, type and #	RA via EHR and H&P	Admission
Partner status	RA via patient	Admission
Education	RA via patient	Admission
Zip code	RA via patient	Admission
Employment	RA via patient	Admission
Smoking status	RA via H&P	Admission
Medications used as outpatient, #	RA via patient	Admission
DNR/I code status	RA via H&P	Admission
Home health aide prior to admission	RA via patient	Admission
Elective and urgent admissions in the previous year, #	RA via patient	Admission
ED visits in the previous 6 months, #	RA via patient	Admission
PRISMA-7	RA via patient	Admission
Eight-item Interview to Differentiate Aging and Dementia	RA via patient or proxy	Admission
Would you be surprised if this patient died in the next year?	RA via MD	Admission
BRIEF health literacy screening tool	RA via patient	Admission
Lives alone	RA via patient	Admission

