6.0 BIOSTATISTICAL ANALYSIS

6.1 Quantitative

Given our small planned enrollment of 3 patients, we will present our quantitative findings either as individual data points or with medians and interquartile ranges. We plan no formal statistical testing.

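### Thirty-day readmissions and ED visits rest on patient report alone, and no endpoint records a death between discharge and day 30

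*Combined protocol and SAP*

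**What the plan says.** The table in section 5.5.2 has two rows for use of care after discharge: "Unplanned readmission(s) after index, # and y/n" and "ED visit(s) after index, # and y/n". Both are timed at "30-days post-discharge", and both name one source, the research assistant asking the patient. No record check, caregiver or proxy is listed for either row.

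Death appears in section 5.5.2 only as unplanned death during the admission. The safety triggers in section 9.0 use the same window, and the adverse event list in the Appendix (section 10.0) does not include death.

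Other sources are used elsewhere. In section 5.5.3, comorbidities come from "RA via EHR and H&P", and the dementia interview may be answered by a proxy. Section 5.5.2 schedules interviews with clinicians, patients and caregivers within a month of discharge. Section 3.3 states: "All subjects will be associated with the University of Utah Health system".

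Eligibility in section 3.1 includes "End of life / desires only medical management". Section 6.1 plans individual data points or medians with interquartile ranges ("Given our small planned enrollment of 3 patients") and adds: "We plan no formal statistical testing". It gives no rule for a patient who has died or cannot be reached at day 30.

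**The concern.** A patient who has died by day 30 cannot be asked about readmissions or ED visits, and one who is too ill may not be able to answer. In both cases the data are missing for a reason connected with what is being measured. The death is not recorded either, because every place in the plan that counts deaths stops counting at discharge.

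The protocol's own population makes this foreseeable. End-of-life patients may enrol, section 5.1 makes provision for patients with stable dementia, and section 5.5.3 asks the physician whether death within a year would be a surprise.

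Safety and quality are secondary aims (section 2.2), and section 1.1.2 says the findings will refine the model and inform its implementation. With three patients, each is a third of the evidence. An unknown that is left out, or a death that no row captures, would make the period after discharge look more complete and more benign than the data support.

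**Working it through.** The plan states no expected event rate, power or non-response rate, so there is no figure of its own to reproduce. The check has three parts.

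**1. Where a post-discharge event could be recorded**

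| Event after discharge | Place in the plan | Recorded if the patient can report? | Recorded if the patient has died or cannot report? |
|---|---|---|---|
| Unplanned readmission | 5.5.2, patient report | Yes | No listed source |
| ED visit | 5.5.2, patient report | Yes | No listed source |
| Death by day 30 | None (5.5.2 and 9.0 stop at discharge; not in the Appendix list) | Not applicable | No row |

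**2. What one or two losses do to a proportion out of 3**

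Inputs: N = 3 (section 6.1). Let m be the number of patients without a report and k the number with an event among those who report. The observed proportion is k/(3 − m). The true proportion lies between k/3 (no missing patient had an event) and (k + m)/3 (all did).

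- m = 1, k = 0: observed 0/2 = 0%; range 0/3 = 0% to 1/3 = 33%.
- m = 1, k = 1: observed 1/2 = 50%; range 1/3 = 33% to 2/3 = 67%.
- m = 2, k = 0: observed 0/1 = 0%; range 0/3 = 0% to 2/3 = 67%.

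Whenever k = 0, the observed value sits at the favourable end of its range. If illness or death is the reason for the missing report, the truth is more likely towards the other end. The documents do not allow that tendency to be quantified.

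**3. How likely at least one loss is**

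Let q be the chance that a patient cannot report at day 30. The documents do not give q, so the values below are assumptions, with patients taken as independent. The chance of at least one loss among three is 1 − (1 − q)³.

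- q = 5%: 1 − 0.95³ = 14%
- q = 10%: 1 − 0.90³ = 27%
- q = 20%: 1 − 0.80³ = 49%
- q = 30%: 1 − 0.70³ = 66%

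Even at modest assumed rates, the situation is plausible enough to plan for.

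**The case against.** A reader might infer more from these rows than they support. Four stronger readings should be set aside.

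- **That outcomes go missing precisely when they are bad.** A patient readmitted and home again before day 30 can report it, and one still in hospital may be reachable, which would itself reveal the readmission. The real gap is death, or being too ill to answer, at the time of contact.
- **That one missed event turns 1/3 into 0/3.** This needs a rule that codes a non-reporter as having no event, and the plan has none. The fair reading is 0/2 plus one unknown. In a listing of individual patients the blank would be visible; in a median it would not be, unless the denominator is shown. Exact 95% intervals (0 to 70.8% for 0/3, 0.8 to 90.6% for 1/3) overlap almost entirely, and the plan reports no intervals, so they add nothing to the argument.
- **That the whole safety summary is biased.** Escalation, adverse events and deaths during the admission are collected daily through the nurse or paramedic and do not depend on the patient.
- **That the EHR would settle the matter.** Section 3.3 ties subjects to one health system but does not say that all their later care happens there. Rural patients may use other hospitals, so patient report is a defensible main source.

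It is also fair to say that the interviews within a month could bring an event to light. They are not a listed source for these rows, however, and a caregiver is not required for a patient to take part. A death after a planned move to hospice may say little about the safety of home care. That is a reason to describe the death, not to leave it without a row. Finally, these are descriptive secondary endpoints in a feasibility study, which limits the weight of the point.

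**Conclusion.** The point holds in a limited form. As written, the plan has no place for a death between discharge and day 30, and no second source for readmissions and ED visits when the patient has died or cannot respond. Such missing data are related to the outcome. With one patient lost and no events in the other two, the observed 0/2 is compatible with anything from 0/3 to 1/3.

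This rests on the source and timing columns being followed as written. How often it would occur is unknown, and the probabilities shown depend on assumed rates. The primary feasibility endpoint and the safety endpoints during the admission are untouched. Section 5.6 adds a related uncertainty: subjects in problematic situations are transferred and formally withdrawn, and that section does not say whether their 30-day outcomes are still collected. The consent terms that bear on this are not in the text reviewed, so this is something to clarify rather than a demonstrated loss. Overall, this is a modest weakness that is worth correcting because the correction costs so little.

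**What to change.** In section 5.5.2:

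- Change the source for both 30-day rows to patient report plus EHR review, with caregiver or proxy report when the patient cannot respond. Keep patient or proxy report in every case, since the EHR may miss care outside the system.
- Add a row for vital status (death from any cause) through day 30 after discharge.
- State that these rows apply to all enrolled patients, including those transferred or withdrawn, where consent allows.

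In section 6.1, state that each patient will be listed for the 30-day outcomes as event, no event, died or unknown, and that unknowns will not be counted as no event.

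The cost is two edited source entries, one new row, two sentences, and a few minutes of chart review for each of three patients. No treatment, eligibility or clinical rule changes. The remaining limitation is that events outside the system in a patient with no available informant may still be unknown; the listing would then show this openly.

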5.5.3 Covariates of Interest

Outcome measure	Data sources	Day(s) Obtained
Age	RA via patient	Admission
Gender	RA via patient	Admission
Race/ethnicity	RA via patient	Admission
Primary language	RA via patient	Admission
Health insurance status, public/private/none	RA via patient	Admission
Comorbidities, type and #	RA via EHR and H&P	Admission
Partner status	RA via patient	Admission
Education	RA via patient	Admission
Zip code	RA via patient	Admission
Employment	RA via patient	Admission
Smoking status	RA via H&P	Admission
Medications used as outpatient, #	RA via patient	Admission
DNR/I code status	RA via H&P	Admission
Home health aide prior to admission	RA via patient	Admission
Elective and urgent admissions in the previous year, #	RA via patient	Admission
ED visits in the previous 6 months, #	RA via patient	Admission
PRISMA-7	RA via patient	Admission
Eight-item Interview to Differentiate Aging and Dementia	RA via patient or proxy	Admission
Would you be surprised if this patient died in the next year?	RA via MD	Admission
BRIEF health literacy screening tool	RA via patient	Admission
Lives alone	RA via patient	Admission

5.6 Standard Operating Procedures for problematic situations

Any subjects presenting with problematic situations will be immediately transferred to the most appropriate hospital and formally withdrawn from the study

Clinically Emergent Patient Condition

Should a matter be emergent, then 9-1-1 will be called and the patient will be brought to the hospital immediately. An example of an emergent patient condition is severe new-onset shortness of breath.

Clinically Urgent Patient Condition

Should a matter be urgent, the patient and/or nurse/paramedic and/or physician may choose to communicate via phone or video (either of the 3 persons can initiate either medium). If this is unsuccessful, the nurse/paramedic will attempt to visit the patient in their home. If there is no way to rectify the situation, then the patient will be transported to the hospital. An example of an urgent situation is new-onset non-severe pain.

Unsafe Home Situation

Should an unsafe home situation be discovered during a home hospital admission, the home hospital team will assess if said situation poses a harm or threat to either the participant or the home hospital personnel. If it does, and after an attempt to rectify said situation, the situation persists, then the home hospital team will end the study and transport the patient to the hospital. An example of an unsafe home situations includes lack of basic sanitation.

Intoxication

Should intoxication occur in the home of a participant, the home hospital team will assess if said intoxication poses a harm or threat to either the participant or the home hospital personnel. If it does, and after an attempt to rectify said intoxication, the situation persists, then the home hospital team will end the study and transfer the patient to the hospital.

Neglect or child abuse

Should neglect or child abuse be observed, the home hospital team will act as mandatory reporters. The home hospital team, in coordination with the hotline team, will assess if said neglect or child abuse poses an immediate harm or threat to either the participant, children in the home, or the home hospital personnel. If it does, then the home hospital team will end the study and transport the patient to the hospital.

Refusal of care

Should an enrolled subject refuse standard care at their home despite a clear discussion with the home hospital team, then the subject will be transferred back to the treating hospital and formally withdrawn from the study.

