1.1.2 Rationale

About 1 in 5 Americans live in rural areas, totaling nearly 60 million people.⁸ Living in a rural area is associated with higher mortality⁹ and poor access to health care, with 23% reporting an average 34-minute drive to their nearest hospital.¹⁰ An acute illness that traditionally requires hospitalization represents a common critical moment in nearly every person’s life. While some in rural areas face intense travel burdens to obtain acute care, others simply go without. Even those who receive care in a hospital may encounter an environment that is unsafe, of poor quality or experience, and expensive.¹¹ This may be particularly true of rural hospitals.^{12,13} In response to this unacceptable geographic disparity, over the last year, our team has designed and refined the rural home hospital (RHH) model through background research, workflow mapping, prototyping, and rapid cycle testing. We conducted a simulation of RHH through a series of “mock admissions” with stable but chronically ill patients in rural Utah. We evaluated the processes, workflows, and technologies involved in RHH and collected qualitative data from the patients, caregivers, and RHH clinical team.

Building on the success of these detailed planning exercises, we propose deploying RHH to care for acutely ill patients in rural and ultra-rural settings in Utah as a proof of concept. This study will evaluate the feasibility and acceptability of the RHH intervention with 3 patients and synthesize key learnings which will be used to refine the RHH model and inform an implementation strategy going forward. If the home hospital model can be successfully deployed in rural and ultra-rural settings, a paradigm shift in access to acute care will occur, providing this care model to rural patients and clinicians.

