2.2 Secondary Aims

Asses RHH for its acceptability, experience, quality, and safety.

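### Section 5.6 withdraws patients from the study when they are transferred to hospital, so the patient-reported post-discharge results would likely cover only those who completed rural home hospital (RHH) care

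*Combined protocol and SAP*

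**What the plan says.** Section 5.6 begins with a rule covering every case beneath it: "Any subjects presenting with problematic situations will be immediately transferred to the most appropriate hospital and formally withdrawn from the study". Six sub-procedures follow.

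- **Emergent condition:** "then 9-1-1 will be called and the patient will be brought to the hospital immediately". Study status is not mentioned.
- **Urgent condition:** phone or video contact, then a home visit, and then "If there is no way to rectify the situation, then the patient will be transported to the hospital". Study status is not mentioned.
- **Unsafe home:** if the problem persists, "then the home hospital team will end the study and transport the patient to the hospital". The neglect or child abuse paragraph ends in the same words.
- **Intoxication:** if the problem persists, "then the home hospital team will end the study and transfer the patient to the hospital".
- **Refusal of care:** the subject is "transferred back to the treating hospital and formally withdrawn from the study".

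Section 5.5.2 schedules the experience questionnaires in the week after discharge, the semi-structured interviews within a month, and readmissions and ED visits at 30 days. The questionnaires and the 30-day outcomes are collected by the research assistant from the patient. The visible text does not say whether these contacts continue after withdrawal, what counts as discharge for a transferred patient, or which patients form the analysis set.

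**The concern.** The rule treats leaving RHH care and leaving the study as the same event. They should be separate. A patient whose home care had to stop can still complete a questionnaire, give an interview and report later hospital use.

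The secondary aim in 2.2 reads "Asses RHH for its acceptability, experience, quality, and safety", and 1.1.2 says the study is to "synthesize key learnings which will be used to refine the RHH model". A patient who had to be moved to hospital, or who refused care at home, speaks directly to both. Under 5.6 that patient is released before any post-discharge measure is due. Whether an experience result exists would then depend on how the home stay went, and what remains would describe only patients for whom it worked. The documents give no basis for the direction or size of any resulting bias.

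**Working it through.** The plan has no power or sample-size figure to reproduce: 6.1 fixes enrolment at 3 patients with no formal testing. The check is therefore a reading of 5.6 against 5.5.2, followed by counts.

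**Reach of the rule (5.6).** Of the six sub-procedures, three end the study (unsafe home, intoxication, neglect or child abuse), one withdraws the subject (refusal) and two say neither (emergent, urgent). Participation is ended explicitly in 3 + 1 = 4 of 6. The other two are reached only through the opening sentence.

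**Outcome rows exposed (5.5.2, 12 secondary rows).**

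| Group | Rows | Count |
|---|---|---|
| Patient only, after discharge | CTM-3, Picker, global satisfaction, 30-day readmissions, 30-day ED visits | 5 |
| Shared post-discharge interviews | Acceptability; safety, quality and caregiver burden | 2 |
| Daily through nurse or paramedic, or from RHH records | Escalation, adverse events, in-admission mortality, lab orders, length of stay | 5 |

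The first group would be lost in full for a transferred patient. The second would lose the patient's part and keep the clinician and caregiver parts. The third does not depend on later contact with the patient. Nor does the primary endpoint (5.5.1), which rests on a daily process checklist and clinician interviews.

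**Entries remaining.** With N = 3 and t transferred patients, the five patient-only rows hold 5 × (3 − t) entries and the three experience questionnaires hold 3 × (3 − t).

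| t | Five patient-only rows | Share of 15 | Three questionnaires |
|---|---|---|---|
| 0 | 15 | 100% | 9 |
| 1 | 10 | 67% | 6 |
| 2 | 5 | 33% | 3 |
| 3 | 0 | 0% | 0 |

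**One yes/no row, one patient missing.** If k of the 2 remaining patients report the event, the figure for all 3 is either k/3 or (k + 1)/3. The range is 1/3, or 33 percentage points, and its direction is open.

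**Chance that it arises.** The documents give no transfer rate, so a per-patient rate p from 2% to 30% is assumed for illustration, with patients independent. The chance of at least one transfer among 3 is 1 − (1 − p)³:

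- p = 2%: 5.9%
- p = 5%: 14.3%
- p = 10%: 27.1%
- p = 20%: 48.8%
- p = 30%: 65.7%

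**The case against.** The strongest reply is that the opening sentence of 5.6 is a loose header. It calls for immediate transfer, yet the urgent, unsafe-home and intoxication paragraphs all try to resolve the problem first. The two paragraphs on clinical deterioration say nothing about study status, and the plan elsewhere treats transfer as an outcome to record (5.5.2) and review (9.0). Withdrawal and ending the study are also undefined and could mean only that the home hospital episode is over. Any terms on data after withdrawal may sit in the consent pages, which were removed before review.

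This supports the word likely and no more. Even on the loose reading, four sub-procedures end participation explicitly, the other two leave study status unstated, and nothing visible keeps the contacts going.

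A second reply is that little is lost. There are 3 patients and no comparator or test, 6.1 already allows individual data points, and a blank would be obvious. Escalation, adverse events and deaths are captured daily, patients are interviewed daily up to transfer (6.2), and clinicians and caregivers can still be interviewed afterwards. All of this stands and limits the weight of the point. However, individual presentation cannot recover data that were never collected, and none of these sources replaces the three questionnaires or the patient-reported 30-day outcomes.

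Third, a transferred patient may have no RHH discharge, so the timing of these rows would be unclear even without the withdrawal rule. Answers given after a hospital stay would also mix two settings. Both points are correct; they shape the fix but do not remove the need for it.

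**Conclusion.** The concern holds and should be fixed. As written, 5.6 would likely leave five of 12 secondary rows empty, and two more partly empty, for any patient transferred for a problematic situation. Each such patient is one third of the planned data in those rows. These are counts of missing entries and do not measure an effect.

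The conclusion assumes that withdrawal is applied in its ordinary sense, that the opening sentence of 5.6 governs the emergent and urgent cases, and that the unseen consent pages do not provide for continued follow-up. Confidence is medium because none of these can be settled from the documents. The primary endpoint stands either way; the exposed part is the patient-reported side of the secondary aim.

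**What to change.** In 5.6, replace the withdrawal and end-the-study phrases with wording to this effect:

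> The patient is discontinued from RHH care but remains in the study. The 1-week, 1-month and 30-day contacts continue unless the patient withdraws consent.

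Add a footnote to 5.5.2 stating that, for a transferred patient, these windows start at final hospital discharge. Report all enrolled patients and list any transferred patient individually.

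The cost is wording at 1 + 3 + 1 = 5 places in 5.6 (the opening sentence, three instances of ending the study, one of withdrawal), the footnote, and one set of research assistant contacts per transferred patient, for at most 3 patients. The drawback is that CTM-3 and Picker answers after a transfer will reflect both RHH and hospital care, which is why those patients should be shown individually and not pooled into a median. If continued follow-up was always intended, the edit simply makes 5.6 say so.
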